Evaluating the use of peppermint oil for postpartum
women with urinary retention

NCT05259800

Document Date: 8/12/2025

RESEARCH PROTOCOL

Date of Protocol	10/11/2021
Title	Evaluating the use of peppermint oil for postpartum women with urinary retention
Principal Investigator	[name], BSN, RN, RNC-MNN
Sub-Investigators	[name], BSN, RN, RNC-MNN; [name], BSN, RN, RNC-MNN
Research Specialist	[name], RN, CPN
Department	Bethesda North Hospital Mom Baby Unit
Hatton #	21-065

Purpose of Study

The purpose of the study is to determine if the use of peppermint oil among postpartum women experiencing urinary retention will increase spontaneous urination and decrease the need for catheterization. Urinary retention is a common occurrence after delivery and can result in discomfort, urinary catheterization, increased risk of postpartum hemorrhage, and increased length of stay. One novel intervention to resolve urinary retention is exposure of the perineum to peppermint oil vapors. This has been studied in four women postoperatively and reported three of the women voided spontaneously after peppermint oil exposure. There were no adverse events reported among these four women (Phillips, 1998). This descriptive study provides preliminary data that peppermint oil could potentially be an effective intervention for urinary retention, but the study had many limitations including a very small sample, a descriptive study without a comparison group, and a heterogenous sample of postoperative women. The current study seeks to build on this by studying the use of peppermint oil among a larger sample of postpartum women experiencing urinary retention using a randomized design.

Hypothesis or Research Question

Hypothesis 1: Postpartum patients with urinary retention who are exposed to peppermint oil will experience a higher frequency of resolution of urinary retention compared to postpartum patients with urinary retention not exposed to peppermint oil.

Hypothesis 2: Postpartum patients with urinary retention who are exposed to peppermint oil will experience a shorter time to spontaneous urination compared to postpartum patients with urinary retention not exposed to peppermint oil.

Hypothesis 3: Postpartum patients with urinary retention who are exposed to peppermint oil will experience an increased volume of spontaneous urine compared to postpartum patients with urinary retention not exposed to peppermint oil.

Hypothesis 4: Postpartum patients with urinary retention who are exposed to peppermint oil will experience a decreased frequency of urinary catheterization compared to postpartum patients with urinary retention not exposed to peppermint oil.

Hypothesis 5: Postpartum patients with urinary retention who are exposed to peppermint oil will experience increased patient satisfaction compared to postpartum patients with urinary retention not exposed to peppermint oil.

Background

Urinary retention is a common occurrence after delivery, resulting in discomfort, pain, and potential need to invasive intervention, including urinary catheterization. Urinary catheterization puts patients at an increased risk for infection, discomfort, and dissatisfaction (Baldini et al., 2009). Anecdotally, peppermint oil vapors have been touted as a noninvasive way to relax muscles and stimulate urination. However, this has not been studied rigorously. Philips (1998) conducted a descriptive study examining the use of peppermint oil vapors in four postoperative women and found that that 3 of the 4 women were able to void spontaneously after being exposed to peppermint oil and no women experienced adverse events. Fryatt and Bell (2020) examined the use of inhaled peppermint oil among 36 pediatric postoperative patients with urinary retention and found a 32% decrease in the need for urinary catheterization among patients who inhaled peppermint oil. While these studies provide interesting preliminary information, a rigorous well-powered randomized trial is needed to truly investigate the use of peppermint oil to stimulate spontaneous urination specifically in postpartum women experiencing urinary retention. The current study seeks to fill this gap.

Research Plan

- **Study Design**

A randomized controlled study will be conducted, with two arms. Subjects will be randomized into one of the two following arms:

- Arm 1: Subjects will be exposed to vapor of peppermint oil
- Arm 2: Subjects will be exposed to vapor of placebo (mineral oil)

- **Setting for the study**

The study will take place in the Bethesda North Mom Baby Unit. This unit consists of 35 rooms. The team members on this unit provide care for patients following delivery. There are approximately 18 women receiving care on this unit each day.

- **Participants**

This study will enroll 100 subjects who meet the inclusion/exclusion criteria.

Inclusion criteria:

1. 18 years old or older
2. English speaking
3. Admitted to Bethesda North Mom Baby Unit
4. Postpartum
5. Experiencing urinary retention – defined as meeting at least one of the following criteria:
 - More than 6 hours after delivery or foley catheter removal without being able to spontaneously void
 - Symptomatic urinary retention without being able to spontaneously void
 - Change in fundal height or position without being able to spontaneously void
6. Bladder scan showing bladder containing 400mL or more urine

Exclusion Criteria

1. Allergy to peppermint
2. Asthma
3. Active herpes lesions
4. Seizure disorder
5. Not able to void in toilet (ex: requiring use of bed pan to void)

Sample Size Determination: A power analysis was conducted using G*Power (version 3.1.9.2). The primary outcome variable (resolution of urinary retention) was used with a medium effect size, power of 0.8, and level of significance 0.05. It was determined that 44 patients would be needed in each group, for a total sample size of 88 patients. Therefore, we plan to enroll approximately 100 patients (50 randomized to each group) to allow for missing data and patient withdrawals.

- **Data Collection**

Before the study begins, the study staff will provide education to team members working in the unit involved in patient care. This education will include information about the study design, the intervention, and the inclusion/exclusion criteria.

Patients who meet the inclusion criteria will be approached by a member of the study team. The study team member will describe the study and answer any questions the patient has. If the patient is interested in enrolling in the study, they will be asked to review and sign an Informed Consent and HIPAA Authorization

Form. Name is included on the Informed Consent Document and name and date of birth are included on the HIPAA Authorization.

After the patient provides written informed consent, the study team member will remove the next envelope out of a box of prefilled and sealed opaque envelopes. The envelope will provide the Subject ID number to be used on all study-related documentation and the study Arm that the patient has been randomized to. All 100 envelopes will be filled before the start of the study using a 1:1 computerized randomization generator.

- **Intervention or experimental aspect of the study**

If the patient is randomized to Arm 1 (intervention group), the study nurse will place 2mL of peppermint oil into the urine collection hat that fits into the toilet bowl. Subjects will sit on the toilet exposing their perineum to the vapor of the oil. The perineum will NOT come into contact with the oil directly. After approximately 10 minutes, the nurse will remove the patient from the toilet. If spontaneous urination occurred, the nurse will measure the volume of urine obtained in the hat. The nurse will calculate approximate volume of urine remaining in the bladder (bladder scan volume minus volume of urine in collection hat). If approximate volume remaining in the bladder is 200mL or greater, the nurse will perform a second bladder scan and follow standard practice for urinary retention.

If the patient is randomized to Arm 2 (control group), the study nurse will place 2mL of mineral oil into the urine collection hat that fits into the toilet bowl. Subjects will sit on the toilet exposing their perineum to the vapor of the oil. The perineum will NOT come into contact with the oil directly. After approximately 10 minutes, the nurse will remove the patient from the toilet. If spontaneous urination occurred, the nurse will measure the volume of urine obtained in the hat. The nurse will calculate approximate volume of urine remaining in the bladder (bladder scan volume minus volume of urine in collection hat). If approximate volume remaining in the bladder is 200mL or greater, the nurse will perform a second bladder scan and follow standard practice for urinary retention.

The voiding procedure using the oil and urine collection hat will be performed only one time with each participant. The study participants won't be explicitly told which group they were randomized into, but the investigators do not consider the subjects to be blinded to group assignment since the smell of the oil will be detectable.

A data collection form will be in the randomization envelope. Data will be recorded directly on this form and collected by a study team member after completion of the study.

Independent variable:

- Whether patient sat on toilet for full 10 minutes

Dependent variables:

- Primary outcome variable – Whether patient spontaneously voided
- Secondary outcome variables:
 - Time that patient spontaneously voided
 - Volume of spontaneous void
 - Whether patient required urinary catheterization or not
 - Patient reported satisfaction with intervention

Potential confounding variables:

- If patient required a second bladder scan, volume of that scan
- Patient's self-reported pain level
- Method of delivery – vaginal or cesarean section
- Whether patient received an epidural or not
- Type of repair
- Whether it was an assisted birth
- Whether patient received duramorph
- Whether patient had foley catheter during stay

- **Statistical Analysis**

Data will be recorded on paper data collection forms with only subject ID and no identifiers. Data from these forms will be entered into a password protected database. Only study team members will have access to the database. No personal information will be entered into the electronic database. Data will undergo range checks when entered in the database, and quality control procedures will be performed to ensure accuracy of the data in the electronic database.

Statistical analyses will be performed using Intellectus Statistics statistical software. Descriptive statistics (frequencies for categorical data; means and standard deviations and ranges for continuous data) will be used to describe the sample. The following analyses will be performed to address each hypothesis:

Hypothesis 1: Postpartum patients with urinary retention who are exposed to peppermint oil will experience a higher frequency of resolution of urinary retention compared to postpartum patients with urinary retention not exposed to peppermint oil.

To compare the effects of the intervention, a Chi Square test will be used to compare occurrence of resolution of urinary retention for patients who received

peppermint oil to patients who did not receive peppermint oil. A level of significance of $\alpha=0.05$ will be used.

Hypothesis 2: Postpartum patients with urinary retention who are exposed to peppermint oil will experience a shorter time to spontaneous urination compared to postpartum patients with urinary retention not exposed to peppermint oil.

To compare the effects of the intervention, an independent samples t-test will be used to compare mean time to spontaneous urination for patients who received peppermint oil to patients who did not receive peppermint oil. A level of significance of $\alpha=0.05$ will be used.

Hypothesis 3: Postpartum patients with urinary retention who are exposed to peppermint oil will experience an increased volume of spontaneous urine compared to postpartum patients with urinary retention not exposed to peppermint oil.

To compare the effects of the intervention, an independent samples t-test will be used to compare mean volume of spontaneous urination for patients who received peppermint oil to patients who did not receive peppermint oil. A level of significance of $\alpha=0.05$ will be used.

Hypothesis 4: Postpartum patients with urinary retention who are exposed to peppermint oil will experience a decreased frequency of urinary catheterization compared to postpartum patients with urinary retention not exposed to peppermint oil.

To compare the effects of the intervention, a Chi Square test will be used to compare occurrence of urinary catheterization for patients who received peppermint oil to patients who did not receive peppermint oil. A level of significance of $\alpha=0.05$ will be used.

Hypothesis 5: Postpartum patients with urinary retention who are exposed to peppermint oil will experience increased patient satisfaction compared to postpartum patients with urinary retention not exposed to peppermint oil.

To compare the effects of the intervention, a Mann Whitney U test will be used to compare patient satisfaction for patients who received peppermint oil to patients who did not receive peppermint oil. A level of significance of $\alpha=0.05$ will be used.

Ethical Considerations

- **Informed consent**

All study staff will complete CITI training. A study staff member will meet with potentially eligible patients and describe the study and answer any questions. If the patient is interested and meets all the inclusion/exclusion criteria, the study staff will review the *Informed Consent and HIPAA Authorization Form* and obtain written informed consent. Patients will receive a copy of their signed Informed Consent and HIPAA Authorization form.

Informed Consent and HIPAA Authorization forms will be stored in a locked area that only study staff will have access to. After the study closes, the signed Informed Consent and HIPAA Authorization forms will be boxed and sent to off-site storage and securely stored for 10 years. At that time, the hard copy forms will be shredded.

- **Privacy information**

Personal identifiers will not be recorded on data collection forms or the electronic database of final data. Hard copy data collection forms will be stored in locked cabinets that only study staff will have access to. Electronic data will be stored on a password-protected folder on the U drive. Only study staff will have access to the electronic study documents. After data analysis and dissemination is completed, hard copy forms will be boxed and sent to secure storage for 10 years at which time they will be shredded. After data analysis and dissemination, electronic data and forms will be de-identified and transferred to a password-protected flash drive which will be sent to secure storage for 10 years at which time it will be destroyed.

Results (8.12.2025)

Between November 3, 2021 and January 29, 2025, 17 patients were enrolled in the research study.

All patients met the following inclusion criteria:

- 18 years old or older
- English speaking
- Admitted to Bethesda North Mom Baby Unit
- Postpartum
- Experiencing urinary retention – defined as meeting at least one of the following criteria:
 - More than 6 hours after delivery or foley catheter removal without being able to spontaneously void
 - Symptomatic urinary retention without being able to spontaneously void
 - Change in fundal height or position without being able to spontaneously void
- Bladder scan showing bladder containing 400mL or more urine

And patients did not have any of the exclusion criteria:

- Allergy to peppermint
- Asthma
- Active herpes lesions
- Seizure disorder
- Not able to void in toilet (ex: requiring use of bed pan to void)

After consenting to participate in the study, participants were randomized (1:1 randomization) to one of two group:

- Intervention Arm: Subjects will be exposed to vapor of peppermint oil (n=10)
- Placebo Arm: Subjects will be exposed to vapor of placebo/mineral oil (n=7)

	Peppermint Oil n=10	Placebo n=7
Scanned Bladder Volume, mL Minimum - Maximum Mean, SD	400 – 941 648.8, 193	424 – 1000 761, 250
Pain Score, 0-10 Minimum - Maximum Mean, SD	0 – 6 2.1, 2	0 – 6.5 2.6, 3

Hypothesis 1:

After 10 minutes of sitting on the hat with the oil (peppermint/mineral), 3 of the participants exposed to peppermint oil voided and 1 of the participants exposed to the placebo voided:

	Voided – Yes	Voided – No
Peppermint Oil	3	7
Placebo	1	6

A Fisher's Exact Test was performed to determine difference in frequency. A level of significance of 0.05 was used. There is no statistically significant difference in frequency of voiding among women exposed to peppermint oil (30%) compared to women exposed to a placebo oil (14%), p=0.603.

Hypothesis 4:

After 10 minutes of sitting on the hat with the oil (peppermint/mineral), 8 of the participants exposed to peppermint oil required catheterization and all 7 of the participants exposed to the placebo required catheterization:

	Required Catheterization – Yes	Required Catheterization – No
Peppermint Oil	8	2
Placebo	7	0

A Fisher's Exact Test was performed to determine difference in frequency. A level of significance of 0.05 was used. There is no statistically significant difference in frequency of requiring catheterization among women exposed to peppermint oil (80%) compared to women exposed to a placebo oil (100%), $p=0.485$.

Hypothesis 5: *Postpartum patients with urinary retention who are exposed to peppermint oil will experience increased patient satisfaction compared to postpartum patients with urinary retention not exposed to peppermint oil.*

A Mann-Whitney U test was used to determine difference in satisfaction between the two groups. A level of significance of 0.05 was used. There was no statistically significant difference in patient satisfaction between participants exposed to peppermint oil ($M=4.4$, $SD=4$) and participants exposed to placebo oil ($M=1$, $SD=0$), $p=0.116$.

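### No adverse event, oil-contact or reason-for-stopping item is listed or reported, so the documents give no harms count by arm

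*Combined protocol and SAP*

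**What the plan says.** Under the intervention heading, the nurse is to "place 2mL of peppermint oil into the urine collection hat that fits into the toilet bowl"; the control arm does the same with mineral oil. For both arms the text adds that "The perineum will NOT come into contact with the oil directly". If the woman voids, "the nurse will measure the volume of urine obtained in the hat", so she voids into the vessel that holds the oil. There is one session of about ten minutes, which the nurse ends.

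On recording, the protocol says "A data collection form will be in the randomization envelope". The form itself is not in the supplied text. The nearest listed item to tolerability is "Whether patient sat on toilet for full 10 minutes", given as the independent variable. The other near item, "self-reported pain level", is a potential confounder with no timing relative to exposure.

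The exclusion criteria cover peppermint allergy, asthma, active herpes lesions and seizure disorder. The documents mention adverse events only for the earlier descriptive study of four postoperative women: "There were no adverse events reported among these four women". The Background repeats this. It cites the pediatric inhalation study for catheterization only.

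**The concern.** The entry criteria show that allergic and respiratory reactions were foreseen, and the no-contact statement is a condition of the intervention. Neither has a matching item after exposure. If the data are confined to the listed variables, nobody can later say how many women in each arm had a new symptom, whether the oil touched anyone, or whether a woman who got up early did so because of the oil.

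The Purpose section criticises the four-woman study for its very small sample and presents this trial as building on it. On its listed variables, the trial cannot give even the harms statement that its predecessor gave. Randomised counts would be worth having because delivery itself causes perineal symptoms, and only a concurrent control arm shows how common they are.

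**Working it through.** The plan gives no harms figure to reproduce, so the check is a reading of the lists followed by simple bounds for scale.

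**Step 1: the listed variables.** There are 14 (1 + 5 + 8).

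| Where listed | Items | Direct harms item? |
|---|---|---|
| Independent variable | Ten-minute completion | No; yes/no without a reason |
| Dependent variables | Spontaneous void, its time, its volume, catheterization, satisfaction | No; efficacy or experience |
| Potential confounding variables | Second-scan volume, pain, delivery method, epidural, repair, assisted birth, duramorph, foley | No; pain is undated and not tied to the oil |

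**Step 2: the analysis.** The Statistical Analysis section gives descriptive statistics for the sample and one test for each of Hypotheses 1 to 5. None of these concerns safety.

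**Step 3: the Results.** "17 patients were enrolled in the research study", 10 on peppermint and 7 on placebo. Reported by arm are scanned bladder volume, pain score, voiding, catheterization and satisfaction. There is no adverse event count, no statement that none occurred, and no count of ten-minute completion. The counts for Hypotheses 1 and 4 are introduced as those after ten minutes on the hat and cover all 10 and all 7 women. That suggests everyone completed the session but does not state it.

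**Step 4: is the list the full record?** No. Scanned bladder volume is reported by arm, but the initial scan is not among the 14 items; only the second scan is. At least one unlisted item was therefore recorded, and a harms field on the form cannot be ruled out.

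**Step 5: what such data could have shown.** Assume, hypothetically, that reactions were recorded and none was seen in n women. The one-sided 95% upper bound is 1 − 0.05^(1/n). The upper limit of the two-sided 95% exact interval is 1 − 0.025^(1/n).

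| Group | n | One-sided bound | Two-sided upper limit |
|---|---|---|---|
| Cited descriptive study | 4 | 1 − 0.473 = 52.7% | 60.2% |
| Placebo, achieved | 7 | 1 − 0.652 = 34.8% | 41.0% |
| Peppermint, achieved | 10 | 1 − 0.741 = 25.9% | 30.8% |
| Each arm, planned | 50 | 1 − 0.942 = 5.8% | 7.1% |

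The n = 4 row uses the zero events reported for the cited study. The other rows are hypothetical, because the documents give no reaction count for this trial.

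**The case against.** The strongest reply is that the variable list sets out analysis roles and is demonstrably incomplete, as Step 4 shows. The form is unseen. The Results are themselves a partial summary: they skip Hypotheses 2 and 3 and most delivery items, so their silence on harms says little about what was collected. All of this stands, and it limits the finding to what is listed and reported. A reader might infer that harms were never collected; the documents do not support that.

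The plan also has real risk controls: the four exclusions and a single short session ended by a nurse. They lower risk but do not count events. A reader might infer that oil reached the skin, or that women reacted or left early. No text reports contact, a reaction or an early exit.

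A reader might also infer that the planned 50 per arm would have let a formal test detect a small excess of reactions. With no placebo symptoms, two-sided Fisher does reach 0.05 at 6/50 (12%, p = 0.027). But a zero background is implausible in recently delivered women, some with repairs, and placebo pain scores run up to 6.5. If 5/50 on placebo had a symptom, peppermint would need 14/50 (28%, p = 0.040). If 10/50 did, it would need 20/50 (40%, p = 0.049). At the achieved size, with 1/7 on placebo, it would need 7/10 (p = 0.0498). These backgrounds are assumptions, but they show why harms counts here should be descriptive, and why a symptom check before exposure is needed.

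Finally, enrolment appears finished and the Results draw no safety conclusion. That makes the point modest but does not remove it: without a sentence on harms, silence may be read as absence.

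**Conclusion.** The point holds as a gap in what is listed and reported. No adverse event, oil-contact or reason-for-stopping item is among the listed variables, and neither the plan nor the Results contains a safety analysis or harms count. This is so although the entry criteria anticipate reactions and the protocol asserts that no contact will occur. Pain, satisfaction, catheterization and ten-minute completion do not substitute, since none identifies a reaction to the oil.

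The size is modest. Safety is not one of the five hypotheses, and no efficacy result changes. With 10 and 7 women, even a complete record with zero events would leave reaction rates up to 25.9% and 34.8% compatible with the data (one-sided 95%). The planned 50 per arm would have brought that to 5.8%. The documents set no threshold for an acceptable rate.

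The finding rests on the supplied text. A harms field on the unseen form would turn it into a reporting gap only. It supports no conclusion about safety in either direction.

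**What to change.** **For the 17 women already treated.** Check the data collection form first. If it holds a harms field, report it by arm. Report the listed ten-minute completion item by arm in any case. If there is no harms field, state that harms were not systematically collected. The cost is one look at the form, one count per arm and at most one sentence.

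**For further enrolment or reuse of the protocol.** Add to the variable list and the form, in both arms, items completed by the attending nurse:

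1. Local and respiratory symptoms just before exposure and again when the woman leaves the toilet, marked as new or worsened (yes/no) with severity.
2. Any observed or reported contact of oil with skin.
3. The reason, if she left before ten minutes.

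Report counts by arm with exact intervals, descriptively and without a significance threshold.

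The cost is a revised form and slightly more form-filling for a nurse who is already present. Symptom reports would be unblinded because the oil can be smelled, and intervals would be wide at small size. The documents do not mention resumed enrolment, so this second part may apply only to a later study.

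### Hypothesis 2 plans a t-test of mean time to void with no time origin, window or rule for women who do not void; over the 10-minute exposure it would compare only voiders, a subset defined by the primary outcome.

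*Combined protocol and SAP*

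**What the plan says.** All references are to the combined protocol and SAP.

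- **Statistical Analysis, Hypothesis 2:** "an independent samples t-test will be used to compare mean time to spontaneous urination", at a significance level of 0.05. The hypothesis is worded for all postpartum patients with retention, not for those who void.
- **Secondary outcome variables:** the variable is listed only as "Time that patient spontaneously voided". No starting point is named.
- **Intervention section:** "After approximately 10 minutes, the nurse will remove the patient from the toilet", and "The voiding procedure using the oil and urine collection hat will be performed only one time with each participant". If the estimated residual is 200 mL or more, a second scan and standard practice follow. How that affects the time variable is not addressed.
- **Independent variable:** the form records "Whether patient sat on toilet for full 10 minutes", but no rule says how a woman who leaves early is analysed.
- **Results, Hypothesis 1:** "After 10 minutes of sitting on the hat with the oil (peppermint/mineral), 3 of the participants exposed to peppermint oil voided", against 1 of 7 on placebo.
- **Results, Hypothesis 4:** "8 of the participants exposed to peppermint oil required catheterization and all 7 of the participants exposed to the placebo required catheterization".
- The Results cover Hypotheses 1, 4 and 5. They contain no result for Hypothesis 2.

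**The concern.** A void time exists only for a woman who voids. The variable list makes spontaneous voiding the primary outcome, so membership of the t-test sample is itself an outcome of treatment. If peppermint oil makes more women void, the additional voiders enter the peppermint mean and have no counterpart in the placebo mean. Randomisation no longer protects the comparison.

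The stake is an estimate that could show slower voiding on peppermint although no woman was slowed, or a small p-value resting on a handful of times. The stake is limited because Hypothesis 2 is secondary.

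**Working it through.** **1. The plan's own figure.** The stated 88 (44 per group) is for the primary outcome. Taking a medium effect as w = 0.3 (the conventional value, assumed), a 1-df chi-square test at alpha 0.05 with noncentrality 88 × 0.3² = 7.92 has power 0.8035. The figure reproduces. No sample size or power is given for Hypothesis 2.

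**2. Who would be in the test.** Voiders at 10 minutes: 3 of 10 and 1 of 7, so 4 of 17. The test would drop 13 of 17 (76%).

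**3. Direction can reverse (assumed times).** Placebo: 35% void, uniformly over 0–10 min (mean 5). Peppermint: the same 35% at the same times, plus 30% who void uniformly over 5–10 min (mean 7.5).

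- Voiders only: peppermint (0.35 × 5 + 0.30 × 7.5) / 0.65 = 4.00 / 0.65 = 6.15 min; placebo 5.00 min.
- All women, non-voiders set to 10: peppermint 1.75 + 2.25 + 0.35 × 10 = 7.50 min; placebo 1.75 + 0.65 × 10 = 8.25 min.

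The voiders-only comparison favours placebo. The all-women comparison favours peppermint, as it should.

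**4. Sensitivity as enrolled (assumed times).** With one placebo voider, the pooled SD comes from the three peppermint values alone.

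- Voids at 2, 2.5, 3 v 9 min: difference 6.5, pooled SD 0.5, SE = 0.5 × √(1/3 + 1) = 0.577, t = 11.26 on 2 df, p = 0.008 in favour of peppermint.
- Voids at 8, 8.5, 9 v 2 min: the same t with the sign reversed, p = 0.008 in favour of placebo.

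Log-rank on all 17 women, z = Σ(O − E) / √ΣV over the four void times:

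- First case: E = 10/17 + 9/16 + 8/15 + 7/14 = 2.184, V = 0.987, z = (3 − 2.184) / 0.994 = 0.82, p = 0.41.
- Second case: E = 10/17 + 10/16 + 9/15 + 8/14 = 2.385, V = 0.962, z = 0.63, p = 0.53.

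**5. Simulated right-direction significance.** 44 per arm, 10-minute window, 5,000 trials per row. The void rates of 65% v 35% are assumed (they correspond to w = 0.3), and every time shape is assumed.

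| Time shape | Voiders-only t-test | t-test, 10 min for non-voiders | Log-rank |
|---|---|---|---|
| Constant hazards | 9% | 75% | 83% |
| Same uniform 0–10 | 3% | 59% | 80% |
| Peppermint 0–7, placebo 0–10 | 49% | 94% | 90% |
| Peppermint 0–5, placebo 0–10 | 94% | 99% | 93% |
| Extra peppermint voids at 5–10 | 0.1% | 23% | 71% |

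In the last row the voiders-only test is significant for placebo in 26% of trials. At the observed rates (30% v 1/7) all figures are lower: log-rank 40% to 48%, the 10-minute t-test 14% to 70%, and the voiders-only test 0.3% to 60%, with 17.5% significant for placebo in the late-void case.

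**6. A longer window.** Fifteen of 17 women were catheterised and only 4 voided, so at least 15 − 4 = 11 of the 13 non-voiders were catheterised: all 6 on placebo and at least 8 − 3 = 5 of 7 on peppermint. If Hypothesis 2 means time to an eventual later void, the plan has no rule for this event.

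**The case against.** **The 10-minute window is not stated.** True. It is the only observation period described, and the Results count voids over it, but the plan neither names it as the window nor states a voiders-only rule. The restriction follows from time being undefined for non-voiders. If the intended variable is time to an eventual void, most women might have a time. The gap then moves to catheterisation.

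**A catheter does not necessarily end time to void.** A reader might infer that catheterisation cuts off any later void time. The documents do not say so. They give neither its type nor its timing, and the inclusion criteria count time from catheter removal, so voiding after a catheter is foreseen. Only the absence of a rule can be claimed.

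**Low power as the flaw.** The simulations tempt this reading, but with some assumed shapes the voiders-only test does well. The objection is the loss of the randomised comparison, which needs no simulation.

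**Early leaving.** The plan says "the investigators do not consider the subjects to be blinded to group assignment since the smell of the oil will be detectable", from which a reader might infer unequal early leaving and one correct way to handle it. No early leaving is reported, and neither handling is unbiased in general. Take 35% voiding in both arms with constant hazards, 44 per arm, and leaving at 1–6 min on peppermint only. If half of those who would not have voided leave, log-rank type I error is about 0.16 with censoring at leaving and 0.05 with leavers counted as not voided. If half leave regardless of later voiding, the figures are about 0.05 and 0.17. These rates support neither rule over the other.

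**Log-rank is partly a preference.** Fair. The t-test with 10 minutes for non-voiders also uses all women and beats log-rank in two of the five shapes at 65% v 35%.

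**Nothing misleading was published.** Also fair. No Hypothesis 2 p-value exists in the Results, any rule is now chosen with void counts known, and 17 women will not give an informative answer.

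**Conclusion.** The point holds as a gap in a secondary analysis that should be fixed. The plan names a test but no origin, window, or rule for non-voiders or catheterised women. Over the single exposure the test compares 3 v 1 voiders of 17, selected by the primary outcome, and its direction can be wrong even when no woman is slower. Calling the subset outcome-defined relies on the variable list and the reported Hypothesis 1, where the primary outcome is spontaneous voiding; elsewhere the plan calls it resolution of retention.

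A reader might infer that the trial's findings are compromised. They are not: no Hypothesis 2 result is reported, and the primary test, the 88 and the conclusion stand. The reversal example and the p-values of 0.008 rest on assumed void times, and the simulated powers on assumed rates and time shapes. Confidence is medium, mainly because the window is inferred and the data collection form is not in the documents, so it is unknown whether start times were recorded.

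**What to change.** Replace the Hypothesis 2 analysis text with:

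> Time to void is measured from the start of exposure in all randomised women, up to 10 minutes. Women who do not void are censored at 10 minutes, and the arms are compared by Kaplan-Meier and log-rank test. Times among voiders are descriptive only.

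Mean time restricted to 10 minutes (the planned t-test with 10 minutes given to non-voiders) is an acceptable simpler alternative. Name one method and label it as chosen after enrolment.

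Also:

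- State how women who leave early without voiding are analysed (counted as not voided, or censored at leaving) and report the other handling as a sensitivity analysis.
- If later voids were timed, state the window and an analysis rule for catheterisation.
- Report Hypothesis 2 on all 17 women, or state that it cannot be estimated if start times were not recorded.

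**Cost:** wording and a rerun on data already collected; no extra patients or procedures. A start time that was not recorded cannot be recovered. The all-women result overlaps largely with Hypothesis 1 (log-rank and chi-square agreed on significance in 87% to 98% of simulated trials across the shapes and rates), so it must not be presented as independent evidence.
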